2.4 Background on the investigation

2.4.1 From the research question

SOS is a multifactorial pathology whose treatment can include multiple topical medications, oral medications, and even surgical procedures. However, ocular lubricants represent the most widely used therapeutic tool by patients with any degree of disease severity. Despite this, there are few comparative studies that allow us to determine the superiority of any lubricant over the rest. [12] However, the properties of each active ingredient provide them with specific characteristics that are exploited to reduce symptoms and signs associated with SOS. There are many commercially available lubricant formulations, so this study aims to test the non-inferiority in efficacy and safety of Humylub Ofteno® PF compared to two other known products, Hyabak® and Lagricel Ofteno® PF.

2.4.2 From the investigational product development phase

Humylub Ofteno® PF is a product that is available for purchase without a prescription in Mexico and Latin America. It has a research and development profile that includes a preclinical *in vivo* safety and toxicity study, as well as a phase I clinical study and a previous phase IV study in which it was compared with Humylub Ofteno® with preservative. See point 2.3 Summary of the pharmaceutical development of Humylub Ofteno® PF.

2.5 Risk-benefit assessment

2.5.1 Known potential risks

Due to the characteristics of the active ingredients of Humylub Ofteno® PF, particularly its high molecular weight and the fact that it is composed of endogenous substances widely distributed in healthy organisms, the occurrence of serious adverse effects related to the investigational product is not expected. The safety profile of both assets, both individually and in combination, has been described in other studies. See points 2.2.1.3 Safety of sodium hyaluronate, 2.2.2.3 Safety of chondroitin sulfate, and 2.3 Summary of pharmaceutical development of Humylub Ofteno® PF.

As with the rest of the topical ophthalmic application formulations, the possibility of mild and transient burning, SCE and blurred vision is anticipated, with a post-instillation duration of no more than one minute. The procedures involved in the execution of this study, and the medications used for them, are also safe and have been described as part of the complete ophthalmological examination.

2.5.2 Known potential benefits

The use of ocular lubricants has been shown to decrease SOS-related signs and symptoms such as burning, SCE, corneal fluorescein uptake, etc. See points 2.2.1.2 Efficacy of sodium hyaluronate and 2.2.2.2 Efficacy of chondroitin sulfate. Patients participating in this study will be exposed to the potential benefit of presenting a significant clinical improvement in the clinical picture related to SOS, with the consequent improvement in their quality of life.

2.6 Problem statement

SOS is a disease that affects millions of people around the world. These patients present a disruption of the homeostasis of their tear film and may suffer multiple signs and symptoms associated with the inadequate protection of their ocular surface due to an insufficient tear in quantity or quality. Although there are multiple therapeutic options available, it is a pathology that continues to be studied due to its great social and economic impact. In addition to seeking therapeutic measures that eliminate the specific etiology of this syndrome, a priority of treatment is to eliminate the symptoms that cause a significant decrease in quality of life. This can be achieved thanks to the use of eye lubricants, whose rheological properties largely determine their effectiveness and safety. It is necessary to continue evaluating the available lubricants to assess their clinical effect and confirm their efficacy and safety in the population exposed to them.

2.7 Justification

The great impact that the diagnosis of SOS represents, both socially, economically and scientifically, has been established, without a doubt; but above all for the quality of life of patients who suffer from it. Epidemiological evidence describes that in some regions the incidence of this disease can reach up to more than 50% of the population. There are currently multiple therapeutic options for the management of SOS, among which ocular lubricants occupy a main place due to their effectiveness in reducing the symptoms associated with the condition and as an aid in the restoration of tear film homeostasis. In the search for the best formulation to manage this type of patient, the rheological properties of substances such as glycosaminoglycans, a family to which both active ingredients of Humylub Ofteno® PF belong, have been used. By combining HS and CS, it is possible to offer patients with SOS symptomatic relief, as well as improvement in signs and alterations related to the vicious circle that characterizes SOS.

Humylub Ofteno® PF is a product that is already marketed, and whose safety profile has already been previously studied; however, it was decided to carry out this study to compare its efficacy with two formulations containing sodium hyaluronate at different concentrations. The intention of this study is to confirm that patients with mild to moderate dry eye find an equal or greater decrease in their

symptoms with the use of Humylub Ofteno® PF, compared to reference products, and to continue in this way to expand the information available on this ophthalmic solution and strengthen its efficacy and safety profile.

3. Objectives and hypotheses

3.1 Primary objective

To demonstrate the non-inferiority of Humylub Ofteno® PF compared to Hyabak® and Lagricel Ofteno® PF in the efficacy of the treatment of patients with dry eye, by means of the OSDI (Ocular Surface Disease Index) test score.

3.2 Secondary objectives

- To demonstrate the non-inferiority of Humylub Ofteno® PF compared to Hyabak® and Lagricel Ofteno® PF in the efficacy of the treatment of patients with dry eye, by means of the measurement of the LRLR.
- To demonstrate the non-inferiority of Humylub Ofteno® PF compared to Hyabak® and Lagricel Ofteno® PF in the efficacy of the treatment of patients with dry eye, by means of changes in corneal and conjunctival stains with fluorescein.
- To demonstrate the non-inferiority of Humylub Ofteno® PF compared to Hyabak® and Lagricel Ofteno® PF in the efficacy of the treatment of patients with dry eye, by changing corneal and conjunctival stains with lysmine green.
- To demonstrate the non-inferiority of Humylub Ofteno® PF compared to Hyabak® and Lagricel Ofteno® PF in the efficacy of the treatment of patients with dry eye, through changes in conjunctival hyperemia.
- To demonstrate the non-inferiority of Humylub Ofteno® PF compared to Hyabak® and Lagricel Ofteno® PF in the safety of the treatment of patients with dry eye, through the incidence of chemosis.
- To demonstrate the non-inferiority of Humylub Ofteno® PF compared to Hyabak® and Lagricel Ofteno® PF in the safety of the treatment of patients with dry eye, through the incidence of AEs.
- To demonstrate the non-inferiority of Humylub Ofteno® PF compared to Hyabak® and Lagricel Ofteno® PF in the safety of the treatment of patients with dry eye, by means of changes in CVAM.

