
 - Changes in the measurement of the TRLNI (ET: visits 1 and final). - Changes of corneal and conjunctival stains with lysmine green (ET: visits 1 and final). - Corneal and conjunctival staining changes with fluorescein (ET: visits 1 and final). - Conjunctival hyperemia changes (ET: visits 1 and final). 	
Safety variables:	

 - Incidence of unexpected AEs related to the research product. (ET: visits 1, final and evaluation) - Changes in the MAVC (ET: visits 1 and final). - Incidence of chemosis (ET: visits 1 and final). 	

Statistical methodology

The Kolmogorov-Smirnov and Shapiro Wilk tests will be performed, as appropriate, to know if the distribution presents normality in the results obtained in each study group. The data will be expressed with measures of central tendency: mean and standard deviation for the quantitative variables. Qualitative variables will be presented in frequencies and percentages. The statistical analysis will be performed by means of the analysis of variance test (ANOVA) for the quantitative variables for the difference between the groups. The difference between the qualitative variables will be analyzed by means of the χ^2 (*Chi-square*) or *Fisher's exact test*. A non-inferiority margin (δ) of 10% will be used for the OSDI score based on the primary endpoint of the study, a $\alpha \leq 0.05$ will be considered significant.

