7.4.2 Secondary outcome variables of efficacy

- Changes in the measurement of the TRLNI. (TE: visits 1 and final).
- Changes of corneal and conjunctival stains with lysmine green (ET: visits 1 and final).
- Corneal and conjunctival staining changes with fluorescein (ET: visits 1 and final).
- Conjunctival hyperemia changes (ET: visits 1 and final).

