10.1.2 Data Interpretation

The Kolmogorov-Smirnov and Shapiro Wilk tests will be performed, as applicable, to determine if the distribution of the data is normal in the results obtained in each study group [56].

The results of the continuous quantitative variables will be presented in measures of central tendency: mean, standard deviation, standard error and/or ranges.

- Intra-group analysis: For equal variances, Tukey's POST-HOC test will be used, otherwise the Dunnett statistic will be used. One-way analysis of variance (one-way ANOVA) will be used when applicable.
- Intergroup analysis: Differences between groups will be analyzed using the Repeated Measures Analysis of Variance (ANOVA) test or the Student's t-statistic when applicable.

A non-inferiority margin (δ) of 10% will be used for the primary efficacy endpoint, based on the primary endpoint of the study. The level of difference to consider significance will be an alpha (α) of 0.05 or less.

The result of the nominal and ordinal qualitative variables will be presented in frequencies, proportions and/or percentages.

The statistical analysis to identify significant differences in the qualitative variables will be carried out by creating 2x2 contingency tables and will be carried out as follows:

- Intra-group difference: McNemar test. This is applied to 2x2 contingency tables with a dichotomous feature, with pairs of paired subjects, to determine if the marginal frequencies of row and column are equal (marginal homogeneity) [7].

- Difference between groups: Pearson's X² (Chi-square) test or Fisher's exact test at expected values less than 5.

The level of difference to consider significance will be an alpha (α) of 0.05 or less.

For the reporting of adverse events, all subjects who were randomly assigned to an intervention group after baseline (intention-to-treat population, ITT) will be considered.

The final report of the results will be shown in tables or graphs, as appropriate.

Variable Type	Variable	A1	B1	B2	C1	D1	D2	D3	D4	E1	E2
Background											
A1	Demographic	DT									
Basal											
B1	Medical History/Selection Criteria	DT									
B2	Comprehensive ophthalmological evaluation	DT				TB	T	T	T	TB	TB
Efficiency											
C1	OSDI	DB			B					TB	
Secondary efficacy outcome											
D1	TRLNI				DB	B				TB	
D2	Corneal and conjunctival stains (TVL and TF)		DT	DT			TB			TB	
D3	Conjunctival Hyperemia		DT	DT		TB				TB	
D4	Chemosis		DT	DT		TB				TB	
Safety											

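### The secondary objectives claim non-inferiority, but they have no margins and are analysed by tests of difference, so the plan has no valid route to those conclusions

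*Combined protocol and SAP*

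**What the plan says.** **Objectives.** Section 3.2 (Secondary objectives) has seven bullets, and each sets out to demonstrate non-inferiority to Hyabak and Lagricel Ofteno PF.
- Four concern efficacy: break-up time, fluorescein staining, lissamine green staining and hyperemia. The hyperemia bullet, for example, claims non-inferiority "in the efficacy of the treatment of patients with dry eye, through changes in conjunctival hyperemia".
- Three concern safety: chemosis, adverse events and visual acuity. They open "To demonstrate the non-inferiority of Humylub Ofteno® PF compared to Hyabak® and Lagricel Ofteno® PF in the safety of the treatment", and the last reads "in the safety of the treatment of patients with dry eye, by means of changes in CVAM".

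The synopsis (section 1.2) lists only six of these and omits visual acuity.

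**Margin.** Section 10.1.2 states: "A non-inferiority margin (δ) of 10% will be used for the primary efficacy endpoint, based on the primary endpoint of the study". The synopsis ties the margin to OSDI: "A non-inferiority margin (δ) of 10% will be used for the OSDI score based on the primary endpoint of the study". The lists of secondary and safety variables in 7.4.2 and 7.4.3 give names and time points only, for example "Changes in the measurement of the TRLNI. (TE: visits 1 and final".

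**Tests.** The variable table in 7.4.4 and section 10.1.2 assign ANOVA or Student's t to the quantitative variables (TRLNI, visual acuity). The qualitative variables (staining, hyperemia, chemosis, adverse events) get 2×2 tables with Pearson's chi-square or Fisher's "exact test at expected values less than 5". The stated purpose of the qualitative tests is to identify significant differences. Alpha is 0.05.

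**The concern.** A non-inferiority conclusion needs a margin fixed in advance and a confidence limit (or an equivalent shifted test) that excludes a deficit of that size. The secondary objectives have neither. A test of zero difference can end in significance or non-significance, and non-significance does not bound how much worse the product might be. As written, none of the seven objectives can be met by the analysis assigned to it.

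The stakes are practical. Section 2.7 says the trial is meant to strengthen the product's efficacy and safety profile, so the claims are intended for use. Three of the seven are safety claims. Section 2.3 reports that in the phase I study fluorescein staining differed significantly at three visits, with more grade 0 cases in the comparator group. Staining is one of the seven endpoints, so a real deficit is a live question.

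**Working it through.** **1. Figures available in the plan.** There is no margin, power or sample size for any secondary objective, so there is no secondary figure to reproduce. The one size calculation (10.2.2) is for OSDI responders: 50 per arm, plus 20% for losses, gives 60. With the stated 30% responder rate, the same rate assumed in the comparator, and the printed formula, n = (2 × 0.30 × 0.70) × [(1.645 + 0.842)/0.10]² ≈ 260, not 50. That is a separate matter for the primary endpoint, and nothing below depends on it.

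**2. Which n applies.** For safety, sections 10.1.2 and 10.1.3 keep all randomised or exposed patients, so 60 per arm is used. For efficacy, section 10.1.5 restricts the analysis to adherent patients and 10.1.4 requires 50 evaluable, so 50 is the cautious figure. (The synopsis and 10.2.1 call all 60 evaluable.)

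**3. One result worked by hand.** Suppose 12/60 (20%) have an event on the test product and 6/60 (10%) on a comparator. The expected event count is 9 per arm, so the plan uses chi-square:
- χ² = 120 × (12 × 54 − 6 × 48)² / (60 × 60 × 18 × 102) = 2.35, p = 0.13, not significant.
- Difference 10 points; SE = √(0.20 × 0.80/60 + 0.10 × 0.90/60) = 0.0645; 95% CI = 10 ± 12.6, that is about −3 to +23 points.

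The test reports no significant difference, while the data are compatible with an excess of more than 20 points.

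**4. How often a true excess is missed.** The rates are assumptions, shown as a range. Setting: one comparison, patient as unit, two-sided 0.05, Fisher when an expected count is below 5 and chi-square otherwise. P(missed) = Σ Bin(a; n, p_test) × Bin(b; n, p_comp), summed over all tables (a, b) that the rule calls non-significant.

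| Comparator vs test | Missed, 60 per arm | Missed, 50 per arm |
|---|---|---|
| 2% vs 8% | 83% | 90% |
| 5% vs 15% | 56% | 65% |
| 10% vs 20% | 67% | 70% |
| 15% vs 25% | 72% | 76% |
| 5% vs 20% | 28% | 36% |
| 10% vs 30% | 20% | 27% |

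**5. Continuous variables.** Three-arm ANOVA, 50 per arm, test product worse than both comparators by d SD; noncentrality = n × d² × 2/3, noncentral F on 2 and 147 degrees of freedom. Missed: 84% for 0.2 SD, 68% for 0.3, 48% for 0.4 and 27% for 0.5.

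**6. Would borrowing the primary margin rescue the claims?** With an assumed 10-point margin, equal true rates p, one-sided 0.025 and 80% power, n per arm = 2p(1 − p) × (1.960 + 0.842)²/0.10². This gives 75 for p = 5%, 142 for 10%, 252 for 20% and 330 for 30%. All exceed 60.

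**The case against.** **A reader might infer that the plan rules a non-significant secondary result to be non-inferior.** It contains no such rule. Section 3.3 does make non-inferiority the null hypothesis, so that failing to reject retains it, but only for the primary OSDI hypothesis. The risk of misreading is still well founded. The plan offers no other route from these tests to the stated objectives, and section 2.3 already draws safety conclusions from earlier non-significant findings. But it remains a risk, not a stated rule.

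**A reader might count fourteen claims (7 × 2 comparators) with no error control.** That is too strong. Each objective joins the two comparators with a conjunction. If success against both is required, there are seven joint claims and no adjustment across comparators is needed; the documents do not say which is meant. Section 10.1.2 also names Tukey and Dunnett procedures, which ordinarily adjust between arms for quantitative variables, though they sit under an intra-group heading. What is absent is any control across endpoints.

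**A reader might infer that non-significance is likely however much worse the product is.** The table shows otherwise: at 60 per arm, power is 0.72 for 5% vs 20% and 0.80 for 10% vs 30%. The problem is with small and moderate deficits.

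**Unit of analysis.** Sections 10.1.3 and 10.2 bring in both eyes. If chemosis were counted per eye and eyes were independent (120 per arm), power for 2% vs 8% would be 0.56, not 0.17. Correlation between eyes puts the true value in between. The per-patient figures are therefore illustrative for eye-level variables.

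**Importance.** These are secondary objectives of a phase IV study of a marketed product, and the sample size rests on OSDI alone. This objection stands and lowers the severity.

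**Conclusion.** The mismatch stands: seven secondary non-inferiority objectives in 3.2, no secondary margin, tests of difference, no confidence-interval rule and no error control across endpoints. The plan has no valid route to these conclusions, and a non-significant result could be misread as one. That much rests on the text alone.

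The size rests on assumed rates. Of the excesses examined, those of 6 to 10 points would be missed 56% to 83% of the time with 60 per arm, and more often with 50. Those of 15 to 20 points would be missed 20% to 28% of the time with 60. The figures assume one comparison and the patient as unit.

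Severity: should be fixed. The primary conclusion does not depend on these claims. The finding does not imply that the primary is free of the same fault: OSDI has a margin, but 7.4.4 also assigns it ANOVA, which needs its own correction.

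**What to change.** 1. Reconcile the lists of secondary objectives in the synopsis (six) and section 3.2 (seven).
2. Reword the secondary objectives as estimating the difference between the test product and each comparator. In 10.1.2, report each difference with a two-sided 95% confidence interval and no non-inferiority claim. Where both eyes are analysed, use a method that allows for the correlation between them. State that a non-significant test will not be taken as evidence of non-inferiority.
3. For any secondary claim the sponsor wants to keep, prespecify a justified margin on that variable's own scale and test it by confidence limit. State whether success against both comparators is required, and place the claim in a fixed order after the primary.

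Steps 1 and 2 change wording and tables only; they need no extra patients, visits or procedures. The cost is that the sponsor gives up claims the design cannot support. Under step 3 a kept claim may well be underpowered: with an assumed 10-point margin and 10% event rates, power at 60 per arm is about 45% (one-sided 0.025).

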3.3 Hypothesis

H_0 = The Humylub Ofteno® PF ophthalmic solution is not inferior in its efficacy compared to its comparators, after 30 days of treatment, presenting a 35% decrease in the final score of the OSDI test compared to its initial value in at least 30% of exposed patients.

$$H_0: P_A - P_B \leq \delta$$

H_1 = The Humylub Ofteno® PF ophthalmic solution is inferior in its efficacy compared to its comparators, after 30 days of treatment, as it does not present a 35% decrease in the final score of the OSDI test compared to its initial value in at least 30% of exposed patients.

$$H_1: P_A - P_B > \delta$$

4. Study design

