1.2 Synopsis

Title of the study:	
Phase IV non-inferiority clinical trial to compare the efficacy of Humylub Ofteno® PF ophthalmic solution against Hyabak® and Lagricel Ofteno® PF on the ocular surface of patients with mild to moderate dry eye syndrome	
Study number: SOPH087-0120/IV	Data created: 15-ene-20
Protocol version: 2.0	Date of version: 27-abr-20
Therapeutic indication: Ocular lubricant	Use: Dry eye
Estimated duration of the study (from the first visit of the first patient to the preparation of the final report): 12 months	Clinical development phase: IV
Objectives: Objective principal: 
 Demonstrate the non-inferiority of Humylub Ofteno® PF compared to Hyabak® and Lagricel Ofteno® PF in the efficacy of treating patients with dry eye, using the OSDI (ocular surface disease index) test score Secondary objectives: 
 Demonstrate the non-inferiority of Humylub Ofteno® PF compared to Hyabak® and Lagricel Ofteno® PF in the efficacy of treating patients with dry eye, through non-invasive measurement of tear breakup time (TBUT). Demonstrate the non-inferiority of Humylub Ofteno® PF compared to Hyabak® and Lagricel Ofteno® PF in the efficacy of treating patients with dry eye, through changes in corneal and conjunctival staining with fluorescein. Demonstrate the non-inferiority of Humylub Ofteno® PF compared to Hyabak® and Lagricel Ofteno® PF in the efficacy of treating patients with dry eye, based on changes in corneal and conjunctival staining with lysamine green. 	

 • Demonstrate the non-inferiority of Humylub Ofteno® PF compared to Hyabak® and Lagrel Ofteno® PF in the efficacy of treating patients with dry eye, based on changes in conjunctival hyperemia. • Demonstrate the non-inferiority of Humylub Ofteno® PF compared to Hyabak® and Lagrel Ofteno® PF in the safety of treating patients with dry eye, based on the incidence of chemosis. • Demonstrate the non-inferiority of Humylub Ofteno® PF compared to Hyabak® and Lagrel Ofteno® PF in the safety of treatment of patients with dry eye, based on the incidence of adverse events (AEs).
Hypotesis:
H_0 = The Humylub Ofteno® PF ophthalmic solution is not inferior in efficacy to its comparators after 30 days of treatment, showing a 35% decrease in the final OSDI test score from baseline in at least 30% of exposed patients.
$H_0: P_A - P_B \leq \delta$

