H_1 = The Humylub Ofteno® PF ophthalmic solution is inferior in efficacy to its comparators after 30 days of treatment, as it does not show a 35% decrease in the final OSDI test score from baseline in at least 30% of exposed patients.
$H_1: P_A - P_B > \delta$
Study design:
Phase IV non-inferiority, controlled, open-label, comparative, multicenter clinical trial.
Number of subjects (planned and analyzed):
Number of patients planned: 60 evaluable patients per arm. Total sample = 180 evaluable patients.
Diagnosis and main inclusion criteria:

 - Patients diagnosed with mild to moderate dry eye.
Selection criteria:
Inclusion criteria:

 - Can voluntarily give their signed informed consent. - Be able and willing to comply with scheduled visits, treatment plan, and other study procedures. - Be of legal age. - Women of childbearing potential must ensure the continuation (initiated ≥ 30 days prior to signing the informed consent form [ICF]) of the use of a hormonal contraceptive method or intrauterine device (IUD) during the study period. - Present a diagnosis of mild to moderate dry eye, defined by an OSDI rating ≥ 13 and one of the following: 
 o Corneal staining with more than 5 sites.

- Conjunctival staining with more than 9 sites.
- Tear film breaking time < 10 seconds.

Exclusion criteria:

[figure not shown]
- Women who are pregnant, breastfeeding, or planning to become pregnant within the study period.
- Have participated in another clinical research study ≤ 30 days prior to the screening visit.
- Have previously participated in this study.
- Have a CVAM of 20/200 or worse in one of the eyes.
- Present an ophthalmological diagnosis of:
 - Allergic, viral, or bacterial conjunctivitis.
 - Blefaritis anterior.
 - Parasitic infestations in any ocular structure or its appendages.
 - Unresolved eye trauma.
 - Healing diseases of the ocular surface.
 - Corneal or conjunctival ulcers.
 - Filamentous keratitis.
 - Neurotrophic keratitis.
 - Bullous keratopathy.
 - Neoplastic diseases on the ocular surface or adnexa.
 - Diseases with fibrovascular proliferations on the conjunctival and/or corneal surface.
 - Retinal and/or posterior segment diseases that require treatment or threaten visual prognosis.
 - Glaucoma.
 - Disorders of the eyelids that cause palpebral malpositions, limit the proper closing or opening of the eyelids, or are the cause of epiphora.

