7.4.4 Definition of variables, methods and scales to be used for the measurement

Variable	Conceptual Definition	Operational Definition	Measurement Type	Normal value	Statistical test
OSDI Score	OSDI is a questionnaire designed to establish a severity and Classification of dry eye according to its symptoms.	The evaluator will apply the questionnaire to the subject and allow the subject to answer it calmly without any pressure and/or coercion. See annex 16.1 OSDI .	Continuous quantitative	Score: OSDI= $\frac{\sum \text{score}}{25}$ n answers answered	
 • ANOVA of repeated measures. • One-way ANOVA*
TRLNI	Measurement of tear rupture time using non-invasive methods based on the observation of the film's mirror reflection in a grating design or in the placid discs of the corneal topographers and their analysis using specialized software.	The TRLNI will be measured by means of the Oculus Keratograph 5M.	Discrete quantitative	>10s	
 • ANOVA of repeated measures. • One-way ANOVA*
Corneal and conjunctival staining with lysmine green	Detection of epithelial defects in the conjunctiva and cornea.	Direct observation with slit lamp, graduation on Oxford scale. See annex 16.2 Oxford scale .	Ordinal Qualitative	Degrees: The stain is presented in a series of panels (A-E). The points Stains range from 0-5 for each panel and from 0-15 for the exposed toral area of the conjunctiva and cornea.	
 • χ^2 (Chi-square) of Pearson or Fisher's Exacta • McNemar Test*

Corneal and conjunctival staining with fluorescein	
Detection of epithelial defects in the conjunctiva and cornea.
	
Direct observation with slit lamp, graduation on Oxford scale. See annex 16.2 Scale of Oxford.
	
Ordinal Qualitative
	
Degrees: The stain is presented in a series of panels (A-E). The points Stains range from 0-5 for each panel and from 0-15 for the exposed toral area of the conjunctiva and cornea.
	
 • χ^2 (Chi-square) of Pearson or Fisher's Exacta • McNemar Test*

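### The worded hypotheses put non-inferiority in H0, the symbols define neither the products nor the sign of δ, and the analysis section ties no test or interval to the 10% margin

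*Combined protocol and SAP*

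**What the plan says.** - **Objective.** Section 3.1: "To demonstrate the non-inferiority of Humylub Ofteno® PF compared to Hyabak® and Lagricel Ofteno® PF", by the OSDI score. Section 2.7 adds: "The intention of this study is to confirm that patients with mild to moderate dry eye find an equal or greater decrease in their" symptoms.
- **Worded hypotheses.** Section 3.3: "H_0 = The Humylub Ofteno® PF ophthalmic solution is not inferior in its efficacy compared to its comparators". The synopsis agrees: "H_0 = The Humylub Ofteno® PF ophthalmic solution is not inferior in efficacy to its comparators after 30 days of treatment", against "H_1 = The Humylub Ofteno® PF ophthalmic solution is inferior in efficacy to its comparators after 30 days of treatment". Both places attach a 35% fall in OSDI "in at least 30% of exposed patients".
- **Symbols.** The synopsis, 3.3 and 10.2.2 all print H0: P_A − P_B ≤ δ and H1: P_A − P_B > δ. Section 10.2.2 defines k, Φ, α, β and δ, and gives δ as an unsigned 10%. It does not say which product is A or B, or what P counts.
- **Margin and tests.** The synopsis attaches the 10% margin to the OSDI score, and 10.1.2 attaches it to the primary endpoint. The between-group tests named are ANOVA, Student's t, chi-square and Fisher's exact, with significance at 0.05.
- **Scale.** Section 7.4.4 classes OSDI as "Continuous quantitative" and assigns it "ANOVA of repeated measures" and one-way ANOVA. Section 10.2.2 sizes the trial on a difference of two proportions.

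**The concern.** In a non-inferiority trial the claim to be shown belongs in H1, so that weak data leave it unproven. With non-inferiority as H0, rejection can only show inferiority, and the claim rests on failing to reject. A small or noisy trial then favours the claim.

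A clear symbolic statement or analysis rule could override the wording, but neither is present. The reader cannot tell which result decides the primary claim, on which scale, or whether it must hold against one comparator or both.

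**Working it through.** **Inputs from the documents.** Margin 10%, α 0.05 with z(1−α) = 1.645 in the formula, power 80% (z = 0.842), expected Humylub response 30%, 50 per arm raised to 60 (all 10.2.2). **Assumed:** comparator 18/60 = 30%, because the documents give no comparator response rate. SE = √[P_A(1−P_A)/n + P_B(1−P_B)/n], the unpooled form in 10.2.2.

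**1. The plan's own figure.** With k = 1, n = [P_A(1−P_A) + P_B(1−P_B)] × [2.4865/(P_A − P_B − δ)]². Section 10.2.2 reports 50 without stating P_B. One pair of figures printed there returns it: P_A = 0.493, P_B = 0.35, δ = −0.10 gives 0.4775 × (2.4865/0.243)² = 49.99, and 50 × 1.2 = 60. Swapping the two and taking δ = +0.10 gives the same 49.99, so reproducing 50 does not reveal A, B or the sign. The pairing is an inference: 49.3% is a mean OSDI reduction and 35% a response threshold, and neither is a responder proportion.

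**2. What the symbols can mean.**
- A = Humylub, δ = −0.10: the usual non-inferiority test, which contradicts the words.
- A = comparator, δ = +0.10: H1 is inferiority by more than 10 points, which matches the reversed words and contradicts the objective.

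**3. Smallest Humylub count accepted, comparator 18/60.**
- Usual form, lower limit above −0.10: 21/60 gives 0.05 − 1.645 × 0.0854 = −0.0905 (met); 20/60 gives 0.0333 − 1.645 × 0.0849 = −0.106 (not met).
- Reversed symbols, H0 retained: 6/60 gives z = (0.30 − 0.10 − 0.10)/0.0707 = 1.41 < 1.645 (retained); 5/60 gives (0.30 − 0.0833 − 0.10)/0.0691 = 1.69 (rejected).
- The worded 30% clause as a point criterion: 18/60 = 30%.
- The worded 30% clause as an exact one-sided 0.05 test of response ≥ 30%: P(X ≤ 12) = 0.057 (not rejected); P(X ≤ 11) = 0.029 (rejected). Accepted from 12/60.

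Against the usual form, the conflicting results are 18–20, 12–20 or 6–20 of 60, depending on the reading.

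**4. Error rate at the margin.** At assumed true rates of 20% on Humylub and 30% on a comparator, exact binomial enumeration of the unpooled z gives:
- reversed symbolic H0 retained: 0.945 at 50 per arm, 0.946 at 60;
- usual test passed: 0.050 and 0.053.

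**5. Power under the usual form, both rates assumed 30%.**
- n = 0.42 × (2.4865/0.10)² = 259.7, so 260 per arm at one-sided 0.05; at one-sided 0.025 it is 330.
- Power per comparison = Φ(0.10/√(0.42/n) − 1.645): Φ(1.091 − 1.645) = 29% at 50 and Φ(1.195 − 1.645) = 33% at 60. At one-sided 0.025 these are 19% and 22%.

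**The case against.** Several points on the other side have force.

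- **The plan does contain a margin test.** The power equation in 10.2.2 uses (P_A − P_B − δ)/SE against z(1−α) and calls δ the test margin. This stands: it would be wrong to say that no margin-based statistic appears anywhere. But it is a sizing formula, δ is unsigned there, and 10.1.2 never adopts it for the analysis.
- **The words do not accept 6/60.** A reader might infer that the worded hypotheses would call Humylub not inferior at 10% against 30%. They do not: 6/60 fails the 30% clause as a point criterion and as an exact test (P(X ≤ 6) = 0.0002). The 6/60 figure belongs only to the symbols read with A = comparator and δ = +0.10.
- **A superiority reading is possible on paper.** With A = Humylub and δ = +0.10, H1 says better by more than 10 points. The plan consistently calls δ a non-inferiority margin, so this reading is not counted.
- **A non-significant test as proof.** A reader might infer that a non-significant ANOVA or chi-square will be reported as non-inferiority. The plan does not say so, so no error rate is charged to that rule.
- **Translation.** The English may be translated, but the reversal appears in both H0 and H1, in two places. Translation would not explain undefined symbols or the missing rule.

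**Conclusion.** The point holds and must be fixed before the primary analysis. The contradiction between objective and worded hypotheses, the undefined A, B, P and sign of δ, the conflict of scale, and the missing link between margin and analysis are all in the text and need no assumption. The clause "in at least 30% of exposed patients" adds a single-arm criterion to a comparative hypothesis, which widens the ambiguity.

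The size of the consequence is conditional. It assumes a comparator at 18/60, a 10-point margin on proportions and one-sided 0.05; on that basis the band of opposite conclusions is 3, 9 or 15 possible counts wide. The contrast of about 95% with about 5% applies to the reversed symbolic reading at 20% against 30%.

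A reader might also infer that the trial is shown to be underpowered. The documents do not support that as a firm conclusion, because the comparator rate is never stated; 260 per arm follows only if it is taken as 30%.

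**What to change.** **Hypotheses (3.3, synopsis, 10.2.2).** Define A = Humylub, B = each comparator in turn, and P = proportion with at least a 35% OSDI decrease at the final visit. State H0: P_A − P_B ≤ −0.10 and H1: P_A − P_B > −0.10. If the OSDI score is the intended scale, write the equivalent pair on that scale. Make the synopsis, 7.4.4, 10.1.2 and 10.2.2 agree.

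**Decision rule (10.1.2).** Conclude non-inferiority only if the lower confidence limit lies above −10 points for both comparators. Say that a non-significant test of difference is not evidence of non-inferiority.

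**Sidedness.** The formula with α 0.05 implies one-sided 0.05, that is, a two-sided 90% interval. Confirm this or declare one-sided 0.025.

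**The 30% clause.** Take it out of the non-inferiority hypothesis and keep it as a planning assumption or a separate criterion.

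**Cost.** This takes a protocol amendment and one interval per comparator. The real cost is that the claim becomes harder to win. The sponsor should state the comparator rate used and restate the power if 80% does not follow from it.
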